8.4. Time Frame for Reporting Required Events

As noted above, minimal adverse events are associated with FDG-PET/MRI. If we are made aware of an AE/SAE, then we will report this to the HRPO in the timeline noted in section 8.2.

9. DATA AND SAFETY MONITORING

In compliance with the Washington University Institutional Data and Safety Monitoring Plan, the Principal Investigator will provide a Data and Safety Monitoring (DSM) report to the Washington University Quality Assurance and Safety Monitoring Committee (QASMC) semi-annually beginning six months after accrual has opened (if at least five patients have been enrolled) or one year after accrual has opened (if fewer than five patients have been enrolled at the six-month mark). This report will include:

- HRPO protocol number, protocol title, Principal Investigator name, data coordinator name, regulatory coordinator name, and statistician
- Date of initial HRPO approval, date of most recent consent HRPO approval/revision, date of HRPO expiration, date of most recent QA audit, study status, and phase of study
- History of study including summary of substantive amendments; summary of accrual suspensions including start/stop dates and reason; and summary of protocol exceptions, error, or breach of confidentiality including start/stop dates and reason
- Study-wide target accrual and study-wide actual accrual
- Protocol activation date
- Average rate of accrual observed in month 1, month 2, and subsequent months
- Expected accrual end date
- Objectives of protocol with supporting data and list the number of participants who have met each objective
- Measures of efficacy
- Early stopping rules with supporting data and list the number of participants who have met the early stopping rules
- Abstract submissions/publications
- Summary of any recent literature that may affect the safety or ethics of the study

The primary study physician and study principal investigator and Research Patient Coordinator will monitor any potential issues on an ongoing basis. Once the principal investigator or Research Patient Coordinator becomes aware of an adverse event, the AE will be reported to the HRPO and QASMC according to institutional guidelines.

10. IMAGE AND DATA ANALYSIS

10.1. Primary objective

The primary objective is to determine technical feasibility of PET/MRI for rectal cancer treatment response assessment and post-treatment surveillance for patients receiving chemoradiation as part of a NOM strategy. Technical feasibility (**the primary endpoint**) will be defined as completion of the PET/MRI rectal cancer protocol with acceptable image quality in $\geq 70\%$ of scans. This proportion is based on a predicted success rate, informed by prior experience with PET/MRI studies. For patients imaged at multiple time points after enrollment (see 7), all available PET/MRIs will be included in the feasibility analysis. Patients able to remain on the scanner for the full duration of the planned data acquisition without any serious adverse events (see 8.1.2) will be considered to have *completed* the PET/MRI rectal cancer protocol. Image quality will be assessed by the Principal Investigator on review at a dedicated workstation with specialized PET/MR software. A standardized Likert-based scoring scheme will be

utilized to capture subjective assessments of image contrast (1 = worst; 5 = best), image resolution (1 = worst; 5 = best), and image artifact ‘freeness’ (1 = worst; 5 = best). Image sets scoring ≥ 3 in all three categories will be considered of *acceptable quality*.

The first imaging session for the first two subjects enrolled will occur with the Principal Investigator present in the scanner control room to direct the tweaking of acquisition parameters and imaging planes in real time. If the Principal Investigator is satisfied with the quality of the reconstructed PET and MR images from these first two cases, as viewed on a dedicated workstation with specialized PET/MR software, the imaging protocol will be considered optimized, and the relevant acquisition parameters will be ‘locked’ as the default for subsequent imaging sessions for these two patients and for all other enrolled subjects. The Principal Investigator will review each of the remaining cases after it is finished (i.e., not in real time but soon after completion) to simulate conditions under which PET/MRI examinations are typically performed (i.e., technologist operating scanner without radiologist present), making an assessment of image quality at that time according to a predetermined qualitative scale.

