4.2. Secondary objective

To estimate the added value of PET/MRI relative to MRI only for detecting residual or recurrent rectal cancer following chemoradiation in patients on an NOM protocol.

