7. STUDY PROCEDURES

Study subjects will be recruited from the population of adult patients referred to Washington University's Radiation Oncology program for an initial biopsy-proven diagnosis of rectal cancer (Enrollment point #1) or previously treated with chemoradiation by Washington University's Radiation Oncology program as part of a NOM strategy for rectal cancer (Enrollment points #2 and #3). Individuals treated with equivalent regimens at other institutions are not eligible. Note that Enrollment point #3 can include patients that have already undergone one or more standard-of-care surveillance imaging sessions. Furthermore, for subjects entering at Enrollment points #2 and #3, there is no requirement that a subject have undergone an FDG-PET examination previously to be eligible.

Patients who meet the inclusion criteria will be recruited to undergo FDG-PET/MRI in lieu of the standard pelvic MRI at ***up to 6 time-points*** at which it would normally be performed in their care for the period of time extending 30-36 months from the time of enrollment (depending on enrollment point). In the surveillance period, when patients typically undergo pelvic MRI every 3 months, the FDG-PET/MRI will be done in lieu of the standard pelvic MRI on an approximately every-other-scan basis. In other words, the FDG-PET/MRI will occur roughly once every 6 months. Target enrollment is 10 patients by the end of year 1 of recruitment and 20 patients by the end of year 2 of recruitment (unless early stopping rule is

satisfied). For subjects entering study at each of the three time points, imaging will consist of the following, assuming no indication for surgery or exclusion criterion is identified:

1. Enrollment point #1 (6 imaging sessions)
 - a. Initial staging FDG-PET/MRI
 - b. Restaging FDG-PET/MRI
 - c. Surveillance FDG-PET/MRI #1
 - d. Surveillance FDG-PET/MRI #2
 - e. Surveillance FDG-PET/MRI #3
 - f. Surveillance FDG-PET/MRI #4
2. Enrollment point #2 (6 imaging sessions)
 - a. Restaging FDG-PET/MRI
 - b. Surveillance FDG-PET/MRI #1
 - c. Surveillance FDG-PET/MRI #2
 - d. Surveillance FDG-PET/MRI #3
 - e. Surveillance FDG-PET/MRI #4
 - f. Surveillance FDG-PET/MRI #5
3. Enrollment point #3 (6 imaging sessions)
 - a. Surveillance FDG-PET/MRI #1
 - b. Surveillance FDG-PET/MRI #2
 - c. Surveillance FDG-PET/MRI #3
 - d. Surveillance FDG-PET/MRI #4
 - e. Surveillance FDG-PET/MRI #5
 - f. Surveillance FDG-PET/MRI #6

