11. STATISTICAL CONSIDERATIONS

The primary endpoint is the feasibility of PET/MRI for rectal cancer treatment response assessment and post-treatment surveillance for patients receiving chemoradiation as part of an NOM strategy. We are interested in the feasibility of PET/MRI for this indication to aid in the planning of a larger prospective trial of short-course radiation therapy followed by adjuvant chemotherapy for the NOM of rectal cancer patients, potentially using PET/MRI to assess for residual or recurrent disease following chemoradiation.

The primary endpoint, feasibility, will be analyzed using descriptive statistics, including exact 95% confidence intervals. Similarly, the secondary endpoint, changes in perceived disease status resulting from the addition to FDG-PET to MRI, will also be analyzed with descriptive statistics, including exact 95% confidence intervals.

A sample size of 20 patients, with an anticipated average of 3 scans/patient, will provide approximately 60 scans for feasibility assessment. If we observe a feasibility rate of 83.3% (i.e., 50 of 60 scans completed imaging sessions with adequate image quality), the exact 95% confidence interval for that proportion and sample size would be 72-92%. The lower limit of this confidence interval will effectively indicate that feasibility is $\geq 70\%$ and that the study has met its primary endpoint.

If a feasibility rate of 90% is observed for the first 20 scans after the optimization phase, the 95% confidence interval for that rate would be 68.3-98.8%. This lower bound will be deemed close enough to 70% to constitute success with respect to achieving the primary endpoint. Thus, enrollment of additional subjects could cease at this point (**early stopping**) at the discretion of the Principal Investigator. Notably, already enrolled subjects would continue receiving additional scans per protocol and will be included in the secondary endpoint analysis.

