12. STUDY CALENDAR

Enrollment point	Screening	Initial staging FDG-PET/MRI	Restaging FDG-PET/MRI	Surveillance #1 FDG-PET/MRI	Surveillance #2 FDG-PET/MRI	Surveillance #3 FDG-PET/MRI	Surveillance #4 FDG-PET/MRI	Surveillance #5 FDG-PET/MRI	Surveillance #6 FDG-PET/MRI
#1	X	X	X	X	X	X	X		
#2	X		X	X	X	X	X	X	
#3	X			X	X	X	X	X	X

Important calendar notes:

- Surveillance scans will not be performed only if a subject undergoes surgery for a suspected recurrence at an earlier time point (see study schema).
- There is no time restriction with respect to when these imaging studies must occur. The FDG-PET/MRIs can occur whenever the subject would have otherwise received an MRI as part of his/her standard-of-care imaging at the designated stages of care as outlined above for each enrollment point.
- Enrollment point #3 can include patients that have already undergone one or more standard-of-care surveillance imaging sessions.

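### One success rate pooled over all scans can declare PET/MRI feasible for response assessment with few, no or mostly failed restaging scans

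*Combined protocol and SAP*

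**What the plan says.** Section 10.1 sets out to determine the "feasibility of PET/MRI for rectal cancer treatment response assessment and post-treatment surveillance for patients receiving chemoradiation" under non-operative management. The endpoint is "completion of the PET/MRI rectal cancer protocol with acceptable image quality in $\geq 70\%$ of scans", and for patients scanned more than once "all available PET/MRIs will be included in the feasibility analysis".

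Section 7 and the calendar in section 12 define three enrollment points, each with six sessions:
- Point #1: one initial staging, one restaging and four surveillance scans.
- Point #2: one restaging and five surveillance scans.
- Point #3: six surveillance scans and no restaging scan. Section 7 adds: "Note that Enrollment point #3 can include patients that have already undergone one or more standard-of-care surveillance imaging sessions".

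The accrual target is 20 patients in total. No section sets a number per enrollment point, a minimum number of restaging scans, or an analysis by scan type.

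Section 11 expects about 60 scans and illustrates success with 50/60, reading the lower exact 95% limit against 70%. It also allows success to be declared early: "If a feasibility rate of 90% is observed for the first 20 scans after the optimization phase", that lower limit is accepted as near enough to 70%.

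The secondary objective (section 4.2) concerns "detecting residual or recurrent rectal cancer following chemoradiation in patients on an NOM protocol". Section 10.2 records the change from mrTRG to pmrTRG over every scan a patient has.

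**The concern.** The conclusion is worded for two uses, but nothing ensures that both are tested. The restaging scan is the first assessment after chemoradiation, and a patient contributes at most one. Surveillance scans can outnumber it several times over, and initial staging scans, which belong to neither use, also count. A pooled rate can therefore be carried by surveillance scans while restaging is barely sampled or performs poorly.

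Section 11 says the result is meant to help plan a larger trial that may use PET/MRI to look for residual or recurrent disease after chemoradiation. A planner relying on PET/MRI at restaging could take over a feasibility statement with little or no evidence at that time point. The pooled grade-change rate is likewise hard to carry forward if it depends on how many patients entered at each point.

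**Working it through.** **Inputs.** 20 patients at an average of 3 scans: 20 × 3 = 60 (section 11). Restaging scans per patient: 1 at points #1 and #2, 0 at point #3 (sections 7 and 12). Thresholds: 70% (section 10.1); 50/60 and 18/20 (section 11). The enrollment mix is not given, so every mix below is an assumption. Like the plan's own intervals, the calculations treat scans as independent.

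**1. The plan's figures.** For x successes in n, the exact limits are the 2.5% quantile of Beta(x, n−x+1) and the 97.5% quantile of Beta(x+1, n−x).
- 50/60: 71.5% to 91.7%. The plan prints 72-92%; the lower limit is 71.48%, an immaterial rounding difference.
- 18/20: 68.3% to 98.8%, as printed.

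**2. Failures tolerated.** 49/60 has a lower limit of 69.6%, so 50 is the fewest successes in 60 with a lower limit of at least 70%. That allows 60 − 50 = 10 failures of any type. Read as a bare observed rate, 70% of 60 is 42, which allows 18.

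**3. Restaging scans available.** The number is at most the entrants at points #1 and #2 combined, so it lies between 0 and 20.

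**4. Limiting cases at 60 scans.**
- All 20 enter at point #3: 0 restaging scans, and 50/60 can still be met.
- 7/7/6 mix: at most 7 + 7 = 14 restaging scans and 60 − 14 = 46 others. If all 46 others succeed, 50 − 46 = 4 restaging successes suffice: 4/14 = 28.6% (exact 95% interval 8% to 58%). On the bare 70% criterion, 46/60 = 76.7% passes with all 14 failed.
- 10 restaging scans, all failed, and 50 good others: 50/60 passes, while restaging is 0/10 (interval 0% to 30.8%).
- The masking is bounded: 11 failed restaging scans give at best 49/60, which misses the lower-limit reading.

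**5. A less extreme case.** Assume true success of 95% for other scans and 50% for restaging. The chance of at least 50/60 (sum of two binomials) is:

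| Restaging scans in 60 | Chance of passing |
|---|---|
| 7 | 0.98 |
| 10 | 0.91 |
| 14 | 0.70 |
| 20 | 0.29 |

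Masking is strong when restaging scans are few and weakens when every patient contributes one.

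**6. Early look.** 18/20 tolerates 20 − 18 = 2 failures. It can be met with no restaging scan, or with two that both failed. Under the rates in step 5, the chance of at least 18/20 is 0.84 with 1 restaging scan among the 20, 0.72 with 2 and 0.57 with 3.

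**7. Secondary endpoint.** No arithmetic is needed. The change rate is pooled over scans, point #3 entrants supply only surveillance scans, and the mix is free. If the true change rate differs between restaging and surveillance, the pooled figure moves with the mix. The documents do not say whether it differs.

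**8. A related inconsistency.** A parenthesis in section 10.2 can be read as saying that the primary endpoint uses only each patient's first scan, contrary to section 10.1. On that reading only point #2 entrants would contribute a restaging scan. The two sections need reconciling.

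**The case against.** The strongest reply is that the endpoint is technical. It scores staying on the scanner without a serious adverse event, and adequate contrast, resolution and freedom from artifact. The scanner and MRI protocol are the same throughout, and acquisition parameters are locked once optimized. Restaging then has little reason to fail while surveillance succeeds. With a common success rate and 50 of 60 successes, the 4/14 split has probability C(14,4) × C(46,46) / C(60,50) = 1,001 / 75,394,027,566, about 1.3 in 100 million. This stands as a limit on how likely the extreme example is. It does not close the gap, because the plan never states or justifies equal success across scan types, and zero restaging scans requires no difference in rates. The possible FDG reduction after a patient's first scan (section 7.2) is only a weak reason to expect a difference: it follows scan order rather than stage, and the plan expects image quality to hold.

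It is also fair that this is a small descriptive pilot, that early stopping ends enrollment only and is discretionary, and that nothing forbids a table by scan type.

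Three stronger readings are tempting but unsupported:
- *Residual disease can be found only at restaging.* Section 10.2 grades regression on every post-treatment scan, and section 3.1 links follow-up imaging to residual as well as recurrent disease.
- *Point #3 patients are selected for sustained response.* Section 12 says only that "Enrollment point #3 can include patients that have already undergone one or more standard-of-care surveillance imaging sessions", which permits earlier surveillance without requiring it. Section 10.2 sends patients without complete response for surgical evaluation, but section 12 drops surveillance scans only if surgery takes place.
- *Section 3.1 shows that disease per scan differs by setting.* One of 9 not in complete response (11%, exact 95% interval 0.3% to 48%) and 1 of 8 later lost (12.5%, 0.3% to 53%) show no difference.

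**Conclusion.** The concern holds as a mismatch between the breadth of the claim and the evidence the plan guarantees. Followed as written, the plan can declare feasibility for both response assessment and surveillance, at 50/60 or at the 18/20 early look, with few or no restaging scans or with most of them failed. The size depends on an enrollment mix the documents do not give: restaging scans may number from 0 to 20, and 0/60 and 4/14 are limiting cases, not forecasts. The documents do not show that restaging is likely to perform worse; they only leave it possible for this to go unseen. For the secondary endpoint the supportable statement is that the pooled change rate mixes restaging and surveillance scans and may depend on the mix.

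**What to change.** In sections 10.1, 10.2 and 11:
- Keep the pooled rate as the primary endpoint.
- Also report the feasibility rate with exact 95% intervals separately for initial staging, restaging and surveillance scans.
- Report the mrTRG-to-pmrTRG change rate with exact 95% intervals separately for restaging and surveillance scans.
- State how many restaging scans lie behind the conclusion.
- Limit the feasibility statement, including any success declared at the early look, to settings actually scanned and supported by their own rate and interval. With no restaging scans, the conclusion does not extend to the restaging time point.

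A per-setting pass mark of an observed 70% is not advisable. It is looser than the lower-limit reading in section 11: 10/14 would pass with an interval of 42% to 92%.

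The change is wording only. Scan type is known from the study calendar, and no patients or scans are added. The cost is wider intervals per setting (for restaging, 6/7 gives 42.1% to 99.6% and 17/20 gives 62.1% to 96.8%) and possibly a narrower claim. Even with 20 restaging scans, a lower limit of at least 70% would need 19/20 (75.1% to 99.9%), so the restaging result should be presented as an estimate with its uncertainty.

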5.2. Exclusion criteria

1. Prior surgical resection of rectal cancer (endoscopic or TME)
2. Contraindication to MRI (see appendix for screening sheet)
3. Comorbidities that would limit patient's ability to cooperate with a PET/MRI examination (e.g. dementia, inability to follow commands, claustrophobia, tremors, requirement for oxygen by nasal cannula, etc...).
4. Implanted devices or materials that may interfere with MRI imaging or create significant artifact
5. Pregnancy
6. Contraindication to gadolinium contrast or FDG
7. End-stage renal disease

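### Pooling only performed scans leaves out PET/MRI sessions missed through refusal or intolerance, so the feasibility rate can overstate repeated surveillance if intolerant patients leave

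*Combined protocol and SAP*

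**What the plan says.** Section 10.1 defines the primary endpoint as "completion of the PET/MRI rectal cancer protocol with acceptable image quality in" at least 70% of scans. Tolerance is part of that endpoint, because completion is credited to "Patients able to remain on the scanner for the full duration of the planned data acquisition without any serious adverse events". For patients scanned more than once, "all available PET/MRIs will be included in the feasibility analysis".

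Section 7 schedules six sessions from each enrollment point, each replacing a standard pelvic MRI, but only "assuming no indication for surgery or exclusion criterion is identified". Exclusion 3 in section 5.2 reads "Comorbidities that would limit patient's ability to cooperate with a PET/MRI examination" and gives claustrophobia and inability to follow commands among its examples.

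On size and analysis, section 11 says "A sample size of 20 patients, with an anticipated average of 3 scans/patient, will provide approximately 60 scans for feasibility assessment", and also "The primary endpoint, feasibility, will be analyzed using descriptive statistics, including exact 95% confidence intervals". Its worked example declares success because the lower confidence limit for 50 of 60 scans lies above 70%.

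Two other places bear on the point. The calendar notes in section 12 give surgery for suspected recurrence as the only reason for omitting surveillance scans. Section 10.2, in passing, describes the primary endpoint of section 10.1 as resting on the first scan alone. No section says how a declined or missed session is to be counted.

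**The concern.** The objective covers treatment response assessment and repeated surveillance, and section 11 uses the answer to plan a larger trial. A patient who cannot stay on the scanner, and who then declines or is judged unable to cooperate, contributes as little as one failure. A patient who tolerates the scan contributes up to six successes. Sessions that the first patient would have had disappear from both numerator and denominator.

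This acts on the point estimate. A cluster-adjusted interval would widen the uncertainty around the pooled rate but would not move the rate back. At stake is whether the study can report that the 70% goal was met while fewer than 70% of the intended PET/MRI sessions were achievable.

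**Working it through.** **1. The plan's own figures.** Exact (Clopper-Pearson) limits for x successes in n scans are the 2.5% quantile of Beta(x, n-x+1) and the 97.5% quantile of Beta(x+1, n-x).

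- 50/60 = 83.3%: 71.5-91.7%. Section 11 states 72-92%; the small difference in the lower limit does not matter here.
- 18/20 = 90%: 68.3-98.8%, as stated.

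**2. Inputs.** From section 11: 20 patients, an average of 3 scans each, about 60 scans. From section 7: at most 6 sessions per patient. Not in the documents, and so assumed: k intolerant patients, each with one failed scan followed by exit; the other 20-k patients each have s acceptable scans; and each intolerant patient would also have had s planned sessions.

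**3. Formulas.**

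- Performed scans (the plan): (20-k)s / [(20-k)s + k]
- Planned sessions: (20-k)s / 20s = (20-k)/20

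**4. Results for s = 4.**

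| k | Performed scans | Exact 95% CI | Planned sessions | Exact 95% CI |
|---|---|---|---|---|
| 3 | 68/71 = 95.8% | 88.1-99.1% | 68/80 = 85.0% | 75.3-92.0% |
| 4 | 64/68 = 94.1% | 85.6-98.4% | 64/80 = 80.0% | 69.6-88.1% |
| 7 | 52/59 = 88.1% | 77.1-95.1% | 52/80 = 65.0% | 53.5-75.3% |

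The k = 7 row gives 13 x 4 + 7 = 59 scans, or 59/20 = 2.95 per patient, close to the plan's expected average of 3. With k = 7 and s = 3 the plan would report 39/46 = 84.8% (71.1-93.7%); with s = 6, 78/85 = 91.8% (83.8-96.6%). Both pass, against 65.0% of planned sessions.

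For k = 1 to 3 and s = 3, 4 or 6, both scan-level rates keep a lower limit above 70%. The lowest is 73.4%, for 51/60 planned sessions at k = 3, s = 3.

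These intervals treat scans as independent, as the plan does, so they are likely to be too narrow when outcomes cluster by patient.

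**5. Relaxing the all-or-nothing model.** A beta-binomial simulation of 20 patients set the true mean success at 70% and let every patient leave after a first failure. The within-patient correlation (ICC) is assumed. The table gives the mean pooled rate over performed scans and the chance that its lower limit reaches 70%.

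| ICC | 3 scheduled scans | 6 scheduled scans |
|---|---|---|
| 0 | 69.5%; 1.5% | 69.2%; 1.5% |
| 0.2 | 73.7%; 7.3% | 76.8%; 24.9% |
| 0.4 | 77.6%; 19.3% | 82.4%; 62.1% |
| 0.6 | 80.9%; 35.7% | 86.7%; 87.0% |

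With nobody leaving, the mean stays at 70% for every ICC. At ICC 0.4 the chance of passing is then 5.3% (3 scans) or 10.5% (6 scans), so most of the excess in the table comes from exit rather than from clustering alone. If half of the patients leave after a failure, the mean pooled rate at ICC 0.4 is 73.9% (3 scans) or 78.1% (6 scans).

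**The case against.** A reader might infer that the protocol drops a patient after one failed session, and hence that the primary result will be biased. The documents do not support that. Exclusion 3 concerns comorbidities, and one aborted session is not itself a comorbidity. The calendar notes in section 12 allow surveillance scans to be omitted only for surgery, and section 10.2 has patients in complete clinical response continue with repeat PET/MRIs. Section 7 makes exit possible and no more. The first failure is still counted, and an image-quality failure need not lead to exit.

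High intolerance is also not the obvious expectation. Claustrophobia and similar problems are screened out at entry, the scan replaces a pelvic MRI that the patient would have had anyway, and the imaging period is capped at 60 minutes. An intolerance share of 35% with certain exit is a harsh case.

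Nor is the matter separate from within-patient correlation: the bias needs both correlation and exit. On the reading in section 10.2 that the primary endpoint is the first scan only, it would not arise. Sections 10.1 and 11 are more explicit for pooling, since about 60 scans cannot come from 20 first scans, but the conflict is real.

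Finally, the endpoint is labelled technical feasibility, and counting refusals brings in acceptance. That is why the planned-session rate belongs beside the per-scan rate and should not silently replace it.

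What stands after all this is that no rule covers declined or missed sessions, and that section 12 does not close the gap because it is silent on refusal and intolerance.

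**Conclusion.** The point holds conditionally. As written, the primary rate ignores sessions not done because of refusal or intolerance, and it gives more weight to patients who keep returning. If intolerance persists within patients and leads to exit, the rate overstates the feasibility of repeated surveillance.

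The size depends on three quantities that the documents do not give: the share of intolerant patients, the within-patient correlation and the probability of leaving after a failure. In the all-or-nothing illustration with four scans per tolerant patient:

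- One to three intolerant patients of 20 leave the verdict unchanged.
- Four put the planned-session lower limit just under 70% (69.6%), although the rate itself is 80.0%.
- Seven turn an apparent 88.1% into 65.0%.

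The documents do not support reading any of these figures as a forecast for this trial. This is a gap to close before the analysis, not a flaw that by itself invalidates the primary endpoint.

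**What to change.** Keep the per-scan rate over performed scans, and add two results beside it in section 10.1.

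(a) *Success per planned session.* A planned session is any staging, restaging or surveillance PET/MRI in the section 7 schedule for the patient's enrollment point that would have replaced a standard-of-care pelvic MRI actually due in the study period. Count it as not completed if it was not done because of refusal, intolerance or inability to cooperate with PET/MRI. Remove sessions no longer due because of surgery, metastatic disease or death.

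(b) *First-scan rate.* Report the proportion of all enrolled patients whose first protocol PET/MRI was completed with acceptable quality. Using all enrolled patients keeps in those who fail a staging scan and leave. With 20 patients this is descriptive: by the plan's own figure, even 18/20 has a lower limit of 68.3%.

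State that the 70% conclusion is to be read together with (a), and record the reason for every missed session prospectively, because it may not be recoverable later.

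Two pairs of passages need to be reconciled: sections 10.1 and 10.2 on whether the primary endpoint uses all scans or the first, and sections 7 and 12 on when later sessions are omitted. Section 7 places surveillance PET/MRI at roughly every second standard scan, and section 12 sets no time restriction. The plan should therefore also say which standard MRIs count as planned sessions for a patient who has stopped PET/MRI.

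The cost is protocol wording, one extra recorded field and a reported rate that may be somewhat lower.
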